5.2 Selection and Timing of Dose for Each Subject

Sodium oxybate has a $t_{1/2}$ of approximately 0.5 to 1 hour. Pharmacologic doses of sodium oxybate have clinical sedative effects that typically last 2 to 4 hours. Sodium oxybate in divided nightly doses has been studied in patients with narcolepsy and patients with fibromyalgia.

Based on pharmacokinetic data demonstrating the generally similar mean concentration-time profiles for JZP-258 and Xyrem under the fasted condition with similar AUC, T_{max} and $t_{1/2}$, and FDA defined bioequivalence under fed conditions, the proposed dose range and timing of dosing of JZP-258 will be similar to Xyrem.

With the following exception, all groups should dose with JZP-258 orally in two equally divided doses taken at bedtime and again 2.5 to 4 hours later. Subjects who entered the study on Xyrem (Pre-randomization Groups 1 and 2) and have used a different nightly dosing regimen prior to study entry, may continue their prestudy dosing regimen throughout the study (i.e. the dosing regimen may consist of two or three equally or unequally nightly divided doses and dosing may begin after the first nightly awakening, however, a once nightly dosing will not be permitted during the study). Subjects entering the study on a different nightly dosing regimen may not change their regimen during the study.

Subjects in all groups will be instructed to take each dose while in bed and remain in bed after each dose. Subjects should take the first dose of study drug at least 2 hours after eating.

Investigators should caution subjects about operating hazardous machinery, including automobiles or airplanes, until subjects are reasonably certain that study drug does not affect them adversely (e.g., impair judgment, thinking, or motor skills). Subjects should not engage in hazardous occupations or activities requiring complete mental alertness or motor coordination, such as operating machinery or a motor vehicle or flying an airplane or going to school alone, for at least 6 hours after taking any dose of study drug.

Confidential Page 47 of 148

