6.13 Adverse Event Reporting

6.13.1 Adverse Events (AEs)

An AE is any untoward medical occurrence associated with the use of a drug in humans, whether or not considered related to study drug or procedure.

Adverse events include, but are not limited to: (1) a worsening or change in nature, severity, or frequency of conditions present at the start of the study (defined as Visit 1 and Visit 18 [Re-entry Subjects]); (2) subject deterioration due to primary illness; (3) intercurrent illness; (4) drug interaction; and/or (5) abnormal clinically significant laboratory values.

- Symptoms of the underlying medical condition narcolepsy are not considered as AEs unless there is an exacerbation of the subject's baseline symptoms at entry into the study. (Visit 1 and Visit 18 [subjects who re-enter the study for the Open-Label Extension]).
- Clinically significant adverse changes from baseline clinical status (Visit 1 and Visit 18 [subjects who re-enter the study for the Open-Label Extension]) in ECGs, routine laboratory tests, and physical examinations are considered AEs. Any subject complaint associated with such an abnormal finding will also be reported as an AE.

All AEs, whether observed by the Investigator, reported by the subject, determined from laboratory findings, or other means, will be documented.

For Re-entry Subjects (completed the Main Study), any new clinically significant condition not previously recorded as an AE during the Main Study and which occurred prior to obtaining informed consent for the Open-Label Extension, is considered medical history and should be documented as such (see Section 6.3).

Subjects should be questioned in a general way, without asking about the occurrence of any specific symptom. The Investigator should attempt to establish a diagnosis of the event based on signs, symptoms, and/or other clinical information. In such cases, the diagnosis, not the individual signs/symptoms, should be documented as the AE.

Following questioning and evaluation, all AEs, whether believed by the Investigator to be related or unrelated to the study drug or procedure, must be documented in the subject's medical records, in accordance with the Investigator's normal clinical practice. Each AE is to be evaluated for duration, severity (Section 6.13.2), seriousness (Section 6.13.3), and causal relationship to the study drug or procedure (see Section 6.13.4).

> Confidential Page 60 of 148

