7.1.5 End of Double-Blind Randomized-Withdrawal Period or Early Termination

End of Week 16 - Visit 16

- Record weight in ordinary indoor clothes (without shoes).
- Obtain vital signs (systolic and diastolic blood pressure, heart rate and respiratory rate, and body temperature) after the subject has been resting for at least 5 minutes.
- Perform a physical examination including a full examination of body systems (excluding a full genitourinary exam) and a brief neurological examination.
- Obtain fasting blood samples for serum chemistry (including Na, K, Ca, and Mg), hematology.
- Collect urine for urinalysis and perform urine drug screen.
- Perform alcohol screen.
- Provide for a light breakfast, if needed.
- Obtain a 12-lead ECG after the subject has been resting supine for at least 5 minutes.
- Complete CGIc for narcolepsy overall.
- Have subject complete the PGIc.
- Obtain a urine pregnancy test for all females of childbearing potential (Section 6.10.1).
- Administer the following:
 - ESS
 - SF-36
 - EuroQoL
 - PHO-9
 - C-SSRS Since Last Visit version.
- Review Cataplexy Frequency Diary for completeness.
- Review the Dosing Diaries for completeness and compliance with dosing.
- Collect remaining study drug from Double-Blind Randomized-Withdrawal Period and assess compliance versus Dosing Diary.
- Record all AEs that occurred since the last visit on the AE eCRF.
- Record all concomitant medications that were taken since the last visit on the concomitant medications eCRF.
- Schedule the Safety Follow-up Visit in 2 weeks if not enrolling into the Open-Label Extension.
- Instruct subject to follow-up with their healthcare provider regarding the resumption of any medications that were discontinued prior to study participation if not enrolling into the Open-Label Extension.

Confidential Page 76 of 148

Jazz Pharmaceuticals

If a subject is withdrawn before completing the study, the reason for withdrawal will be entered on the appropriate eCRF. The specific reason for the withdrawal should be documented on the eCRF. For instance, rather than stating "withdrew informed consent", the specific reason for withdrawing the informed consent should be stated. Whenever possible and reasonable, the evaluations that were to be conducted during the final study visit should be performed at the time of premature discontinuation.

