## 9.9. SAFETY OUTCOMES

In general, safety outcomes will be summarized across all study periods by visit overall, and by Pre-Randomization Group based on SAF. Data collected while subjects randomized to placebo were on placebo will be excluded from this summaries.

Data will also be summarized overall and by treatment group based on the DB RWP SAF.

No inferential statistics will be performed; only summary statistics will be provided unless otherwise noted.

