### 9.9.1. ADVERSE EVENTS

AEs will be coded to SOC and PT using the MedDRA dictionary, version 19.1 and will be classified as follows:

- **Prior AEs** are defined as AEs that started on or after the signature of the Main Study informed consent but prior to the first dose of OL OTTP study drug;
- **For the overall summaries**, (TEAEs) are defined as any AEs that started or worsened in severity on or after the first dose of Open-Label study drug up to the last dose of study drug during the Open-Label Optimized Treatment and Titration period, Open-Label Stable-Dose Period, Double-Blind Randomized-Withdrawal Period or Open-Label Extension period (whichever is the latest) + 30 days.
- **For the DB RWP**, TEAEs are defined as any AEs that started or worsened in severity on or after the first dose of double-blind study drug up to 1) the last dose of double-blind study drug for subjects who did not enter the Open-Label Extension, 2) the first dose of study drug during the Open-Label Extension for subjects who rolled over into the Open-Label Extension immediately

after having completed the Main Study or 3) whichever occur first between the following two timepoints for subjects who rolled over into the Open-Label Extension after having re-entered into the study: last dose of double-blind study drug or first dose of study drug during the Open-Label Extension.

- **For the Main Study**, TEAEs are defined as any AEs that started or worsened in severity on or after the first dose of study drug up to the first day of the Open-Label Extension period for rollover subjects; or the first day of the Open-Label Extension period or the day of the last dose of study drug in the Double-Blind Randomized-Withdrawal period + 30 days (whichever is the earliest) for re-entry subjects.
- **For the OLE**, TEAEs are defined as any AEs that started or worsened in severity on or after the first dose of Open-Label study drug during the Open-Label Extension period up to the last dose of study drug + 30 days.
- **Post AEs** are defined as any AEs that started or worsened in severity after the last dose of study drug during the OTTP, SBP, RWP or OLE (whichever is the latest) + 30 days.

For OLE re-entry subjects, AEs occurring after their last dose of DB study drug, but prior to their first dose of OLE study drug will be considered as post AEs .

Only TEAEs will be summarized, but all AEs will be presented in the subject data listings.

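### The double-blind TEAE window ends at the last dose for some subjects and at the first OLE dose for others, so capture of late adverse events in the by-arm summary depends on route after the period

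*SAP*

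**What the plan says.** SAP 9.9.1 sets three end points for a DB RWP TEAE:

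- **Never in the OLE:** "the last dose of double-blind study drug for subjects who did not enter the Open-Label Extension".
- **Direct rollover:** "the first dose of study drug during the Open-Label Extension for subjects who rolled over into the Open-Label Extension immediately" after the Main Study.
- **Re-entry:** whichever comes first of "last dose of double-blind study drug or first dose of study drug during the Open-Label Extension".

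The same section adds, for re-entry subjects, that "AEs occurring after their last dose of DB study drug, but prior to their first dose of OLE study drug will be considered as post" events. It tabulates TEAEs only; other events appear in listings. Its overall and OLE definitions, and the algorithm in SAP Appendix 2, allow 30 days after the last dose. The DB RWP definition allows none.

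SAP 9.9 plans by-treatment-group safety summaries on the DB RWP safety population. The across-period summaries are overall and by Pre-randomization Group, and for these "Data collected while subjects randomized to placebo were on placebo will be excluded from this summaries".

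The protocol doses in "two equally divided doses taken at bedtime and again 2.5 to 4 hours later" (Section 5.2, with an exception for some subjects already on another nightly regimen). At Visit 16 or Early Termination, Section 7.1.5 schedules the physical examination, fasting laboratory tests and ECG ("Obtain a 12-lead ECG after the subject has been resting supine for at least 5 minutes"). Under Section 6.13.1, clinically significant adverse changes in ECGs, "routine laboratory tests, and physical examinations are considered AEs".

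**The concern.** In a randomized comparison of adverse-event incidence, both arms should be observed over a window fixed by design. Here the end of the window depends on what the subject does after randomization: roll over directly, re-enter later, decline the OLE, or stop early. Part of that is calendar time, since subjects who finished double-blind treatment before Amendment 4 was approved could only re-enter (Protocol 3.1.2.1). Part is outcome, since stopping early rules out the OLE.

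The events exposed to this rule are not a random sample. They are events noticed after the drug is stopped, and clinically significant findings from end-of-period tests. After screening, the Main Study repeats the ECG, physical examination, hematology, full chemistry and urinalysis only at Visit 16 or Early Termination (Protocol 6.6, 6.10.2, Appendix 1.1). Safety is a stated secondary objective, and the by-arm summary is where JZP-258 is set against placebo. The DB RWP counts of serious TEAEs and of TEAEs leading to discontinuation inherit the same window.

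**Working it through.** The plan gives no figure to reproduce, so the check applies the stated rules to each type of subject.

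**Inputs.** Number the double-blind days so that the first dose is on day 1. Assume 14 dosing nights, so the last bedtime dose is on day 14, with Visit 16 on day 15. The second nightly dose may fall after midnight, so the last-dose date is day 14 or day 15; the SAP does not say which. For a re-entry subject take a first OLE dose on day 60 for illustration; any date after the last double-blind dose gives the same answer. The day-18 event stands for a finding at a visit held after dosing stopped on day 14 or 15.

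**Rule.** Window end = last-dose date (never OLE); min(last-dose date, first OLE dose date) (re-entry); first OLE dose date (rollover). An event counts if its onset date is on or before the window end.

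| Last dose dated | Subject | Window end | Onset day 14 | Onset day 15 | Onset day 18 |
|---|---|---|---|---|---|
| Day 14 | Never OLE | 14 | in | out | out |
| Day 14 | Re-entry | min(14, 60) = 14 | in | out | out |
| Day 14 | Rollover | 15 (18 if Visit 16 is on day 18) | in | in | in |
| Day 15 | Never OLE | 15 | in | in | out |
| Day 15 | Re-entry | min(15, 60) = 15 | in | in | out |
| Day 15 | Rollover | 15 (18 if Visit 16 is on day 18) | in | in | in |

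Three results follow.

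1. For re-entry subjects the earlier date is always the last double-blind dose, so they are treated like subjects who never enter the OLE.
2. An onset after the last-dose date is excluded for both of those groups and included for rollovers. For an early terminator with last dose on day L and a finding dated day V > L, exclusion is certain under either dating rule.
3. Every excluded event in the table lies inside last dose + 30 days (14 + 30 = 44; 15 + 30 = 45), the lag used in the overall and OLE definitions.

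**Against the plan's other windows.** SAP Table 2 assigns unscheduled and Early Termination laboratory and ECG data to the DB RWP up to the date of Visit 16. A value can therefore be double-blind data while the adverse event raised from it is not a double-blind TEAE. Protocol 9.11.1 bases by-period summaries on events emergent within the period and sets no cut at the last dose. Within SAP 9.9.1, the Main Study definition counts re-entry events up to 30 days after the last double-blind dose (or to OLE day 1 if earlier), whereas the sentence quoted above calls the same events post AEs.

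**With the proposed end point.** Last dose on day 14, Visit 16 on day 15: max(14 + 1, 15) = 15. Visit on day 18: max(15, 18) = 18, inside 14 + 30 = 44. Last dose on day 15, visit on day 18: max(16, 18) = 18, inside 45. All events in the table are now in for the never-OLE and re-entry rows, and the rollover rows do not change because the first OLE dose still cuts them off.

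**The case against.** A reader might infer that reactions to the final dose drop out by definition, because they follow that dose. The documents do not support that. The window is inclusive of the last dose, and the SAP Appendix 2 algorithm compares dates, not clock times. A reaction on the last-dose date is counted. If a second dose after midnight sets that date, an event dated at a Visit 16 held the same day is counted too.

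For the same reason, two tempting figures fail. One is that a non-rollover completer loses the events of one dosing night in 14 (1/14 = 7.1%). The other is that all events first found at Visit 16 are lost. The first also confuses nights with incidence, since a preferred term counts once per subject. The second assumes that the last-dose date precedes Visit 16 and that onset is dated to the test; neither is stated.

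More can be said for the plan. Laboratory summaries, including shift tables, are repeated by treatment group on the DB RWP safety population (SAP 9.9.2), so Visit 16 abnormalities stay visible as values. All adverse events are listed, by default in randomized-arm order (SAP Appendix 1), and the listings of deaths and serious events are not limited to TEAEs. Events in never-OLE subjects remain in the overall 30-day window. That the DB RWP summary is the only by-arm adverse-event table is an inference from SAP 9.9: the columns of the separate Main Study TEAE summary are not stated, and the table shells are not in the documents. For completers the difference from rollovers is about one day, and the SAP expects few double-blind discontinuations (9.8.1.5). Safety analysis is descriptive, and no between-arm bias has been shown.

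All of this stands, and it limits the size of the problem. It does not remove the unequal window, and the undefined last-dose date is itself a reason to tighten the text.

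**Conclusion.** The concern holds as a defect in a stated rule. Adverse events with onset after the last double-blind dose date count in the by-arm DB RWP summary for direct rollovers and for nobody else, and early terminators are always truncated. This is certain for a finding dated at an Early Termination visit after dosing stopped. For Visit 16 it holds only where the last dose carries the previous evening's date.

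The number of events affected cannot be calculated from the documents and is probably small for completers. The conclusion assumes date-level comparison, as in SAP Appendix 2, and the reading of SAP 9.9 that the arms are compared on the DB RWP safety population. It does not claim that the arms are affected unequally. The change is worth making before unblinding because it is cheap and removes a dependence that would be awkward to explain afterwards.

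**What to change.** In SAP 9.9.1, replace the three DB RWP end points with one for all randomized subjects. Count events that start or worsen from the first double-blind dose through the later of (a) the last double-blind dose date + 1 day and (b) the Visit 16 or Early Termination date. State a maximum lag for late Early Termination visits, for example within the 30 days the SAP uses elsewhere, and cut off at the first OLE dose.

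With it:

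- State how the last-dose date is set when the second nightly dose falls after midnight, and that the comparison is by date.
- Apply the window to the DB RWP summaries of serious TEAEs and of TEAEs leading to discontinuation.
- Reconcile the sentence that classes re-entry events after the last double-blind dose as post AEs, both with the new window and with the Main Study definition. That definition also needs an end date for subjects who never enter the OLE.

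The cost is a short SAP edit and one derivation, with no new data collection. The downside is that a few off-drug events between stopping and the Early Termination visit will be attributed to the double-blind arm; the maximum lag keeps that number bounded.

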9.11.1 Adverse Event Analyses

Adverse events will be mapped to system organ classes and preferred terms using the Medical Dictionary for Regulatory Activities (MedDRA).

The subject incidence of TEAEs, TEAEs related to study drug, SAEs, AEs leading to discontinuation, and fatal AEs will be summarized. This overall summary will also provide TEAEs by maximum severity.

The subject incidence of TEAEs, TEAEs related to study drug, AEs, and AEs leading to discontinuation will also be presented by system organ class and preferred term. Preferred term summaries may also be provided.

A TEAE is defined as an AE that either began after the first study drug dose or worsened after the first dose. In summarizing the subject incidence of AEs, multiple events with the same preferred term or with increases in severity will only be counted as one AE and summarized at the maximum severity. Subject incidence is similarly defined for multiple events within the same system organ class. Summaries by period will be based on AEs considered emergent within a period.

Adverse events occurring after a subject has completed the Main Study and prior to the Open-Label Extension Period will be recorded as medical history. Adverse events occurring after first dose of study drug in the Open-Label Extension Period will be considered treatment emergent.

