In addition, TEAEs will be summarized for the Main Study and OLE separately.

An overall summary of the number and percentage of subjects within each of the following categories will be provided:

- All TEAEs
- TEAEs with a severity of severe
- Life-threatening TEAEs
- Fatal TEAEs
- TEAEs related to study drug
- TEAEs with an outcome of death
- Serious TEAEs
- TEAEs leading to discontinuation of study drug

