**ALGORITHM FOR TREATMENT EMERGENCE OF ADVERSE EVENTS**

START DATE	STOP DATE	ACTION
Known	Known, Partial, Missing	
 
• If AE start date or worsened in severity < study drug first dose date, then not TEAE
 
• If study drug first dose date ≤ AE start date or worsened in severity ≤ (study drug last dose date + 30 days), then TEAE
 

Partial, but known components show that it cannot be on or after study drug first dose date	Known, Partial, Missing	Not TEAE
Partial, but known components show that it could be on or after study first dose date	Known	
 
• If AE stop date < study drug first dose date, then not TEAE
 
• If study drug first dose date ≤ AE worsened in severity or stop date ≤ (study drug last dose date + 30 days), then TEAE
 

or	Partial	If known components show that: 
 
• AE stop date < study drug first dose date, then not TEAE
 
• {[Study drug first dose date ≤ AE stop date ≤ (study drug last dose date + 30 days)] or [(study drug last dose date + 30 days) < AE stop date]}, then TEAE
 

Missing	Missing	Assumed TEAE

Note: Missing days will be assumed to be the first day of the month and missing months will be assumed to be the first month of the year for the purposes of determining if a partial date could be on or after the study first dose date (i.e. first day of month if day unknown or 1st January if day and month are unknown),.

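### SAP 9.9.1 gives two incompatible classes to adverse events that OLE re-entry subjects report in the off-drug weeks after the double-blind period

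*SAP*

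**What the plan says.** SAP 9.9.1 sets several windows for AEs. Those that matter for re-entry subjects are:

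- **Main Study TEAEs.** The window opens at the first dose. For these subjects it closes at the first day of the OLE or "the day of the last dose of study drug in the Double-Blind Randomized-Withdrawal period + 30 days (whichever is the earliest) for re-entry subjects".
- **Closing re-entry sentence.** AEs of the same subjects "occurring after their last dose of DB study drug, but prior to their first dose of OLE study drug will be considered as post AEs".
- **Overall TEAEs.** The window closes 30 days after the latest last dose over all periods: "Double-Blind Randomized-Withdrawal Period or Open-Label Extension period (whichever is the latest) + 30 days".
- **General post AEs.** These start or worsen "after the last dose of study drug during the OTTP, SBP, RWP or OLE (whichever is the latest) + 30 days".
- **Double-blind period TEAEs.** For re-entry subjects the window ends at the last double-blind dose.

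On reporting, the section states: "Only TEAEs will be summarized, but all AEs will be presented in the subject data listings". SAP 9.9.1 also plans a Main Study table: "In addition, TEAEs will be summarized for the Main Study and OLE separately".

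The treatment-emergence algorithm in SAP Appendix 2 applies the condition "AE start date or worsened in severity ≤ (study drug last dose date + 30 days), then TEAE". It has no re-entry exception and does not say which period's last dose is meant.

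Protocol 9.11.1 defines a TEAE by onset or worsening after the first dose and gives no closing date. It adds: "Adverse events occurring after a subject has completed the Main Study and prior to the Open-Label Extension Period will be recorded as medical history".

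Re-entry subjects are a defined group: those who finished double-blind treatment before Amendment 4 had regulatory approval (Protocol 3.1.2.1).

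**The concern.** Two rules in one section both name re-entry subjects and assign the same event to different classes. Neither can be read as the general case with the other as its exception, because both are already specific to this group. If the closing sentence governs, the 30-day clause in the Main Study bullet never operates for the subjects it was written for.

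The programmer has to choose, and the choice decides whether AEs from the safety follow-up appear in the summary tables (incidence, severity, relatedness, serious, special interest) or only in listings. Under the closing sentence, the class of an event at, say, day 10 would depend on whether the subject later came back for the OLE. The same event in a subject who never enters the OLE is a TEAE under the overall bullet.

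**Working it through.** The plan states no figure to reproduce. The check compares the windows.

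**Step 1: overlap in days.** Let day 0 be the last double-blind dose and day g the first OLE dose, taken as OLE Day 1. The documents do not give g, so the values below are assumptions. Visit 19 is only for subjects who completed Visits 16 and 17 (Protocol 7.2.1.3), and Visit 17 comes two weeks after the double-blind period, so g is about 14 days or more.

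- Main Study TEAE: days 1 to min(g, 30)
- Closing sentence, post AE: days 1 to g − 1
- Both: days 1 to min(g − 1, 30)

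| g | Main Study TEAE | Post AE (closing sentence) | Days under both rules | Days post AE only |
|---|---|---|---|---|
| 15 | 1–15 | 1–14 | 14 | 0 |
| 20 | 1–20 | 1–19 | 19 | 0 |
| 31 | 1–30 | 1–30 | 30 | 0 |
| 45 | 1–30 | 1–44 | 30 | 44 − 30 = 14 |
| 60 | 1–30 | 1–59 | 30 | 59 − 30 = 29 |

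The rules clash for every possible gap.

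**Step 2: are AEs recorded in the overlap?** Yes. The Main Study includes the two-week safety follow-up (Protocol 3.1.1), and Visit 17 records all AEs before the subject is discharged (Protocol 7.1.6). The medical-history rule in Protocol 9.11.1 starts only after Main Study completion, and SAP 9.3 draws its own line at the same visit. After Visit 17 less is recorded as an AE: SAEs learned of within 30 days of the last dose, and AEs after consent at Visit 18 (Protocol 6.13.6).

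**Step 3: three example events, g = 60.** For the overall bullet and Appendix 2, the last dose is taken as the last OLE dose.

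| Event | Overall bullet, Appendix 2 | Main Study bullet | General post-AE bullet | Closing sentence | After the fix |
|---|---|---|---|---|---|
| AE, day 10 (Visit 17) | TEAE | TEAE | not post | post | TEAE |
| SAE, day 20 | TEAE | TEAE | not post | post | TEAE |
| AE, day 45 (after Visit 18 consent) | TEAE | not TEAE | not post | post | post |

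**Step 4: size.** The number of re-entry subjects is not given. As an illustration only, suppose 5% to 15% of them have a new AE in the two weeks to Visit 17; this range is an assumption with no source in the documents. Then 10 × 0.05 = 0.5 to 10 × 0.15 = 1.5 subjects per 10 re-entry subjects would change class.

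**The case against.** **The general rules are not true contradictions.** A reader might infer that the closing sentence contradicts every other AE rule. The documents do not support that. The overall bullet, the general post-AE bullet and Appendix 2 are general rules, and a later sentence about one subgroup is naturally read as an exception to them. The SAP treats re-entry subjects by exception elsewhere too (9.3, 9.4, 9.5). This stands: the only direct clash is with the Main Study bullet. What remains is that the general rules do not carry the exception.

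**The protocol gives direction.** It would also be too strong to say that the protocol leaves the matter open. Protocol 9.11.1 has no upper cut-off for TEAEs and sends only events after Main Study completion to medical history. The day-10 event is therefore a TEAE on the protocol's terms, and SAP 3.6 declares no departure from this. This also stands, and it counts against the closing sentence.

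**Excluding the gap is defensible.** Oxybate has a half-life of about 0.5 to 1 hour, and subjects who do not roll over may resume other treatment after Visit 16. Ending the Main Study window at the last double-blind dose would also remove the clash. But the pharmacological argument applies equally to subjects who never enter the OLE, and the overall bullet keeps 30 days for them. That remedy would still make the class depend on later re-entry and would drop events that the protocol's definition includes.

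**Placebo subjects.** SAP 9.9 removes on-placebo data from the across-period summaries but does not address events after placebo stops. This is a fair open question. It concerns all placebo subjects who do not roll over, and the fix does not create it.

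**Unseen shells.** The table shells mentioned in SAP 8 are not available and may state the windows.

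**Conclusion.** The contradiction is real and lies in the text of SAP 9.9.1. It affects only re-entry subjects, from day 1 after the last double-blind dose to the earlier of day 30 and the day before the first OLE dose. The protocol supports counting events up to Visit 17 as TEAEs. From there to day 30 the support is the SAP's own 30-day window.

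The consequence is minor: descriptive counts in the Main Study and overall TEAE tables, in a restricted group of unknown size. A reader might infer that the randomized safety comparison is distorted or that events are lost. Neither follows. The double-blind window already closes at the last double-blind dose for these subjects, all AEs are listed, and SAEs and deaths have their own listings. No efficacy analysis or error rate is touched.

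The point is worth correcting because the text is wrong as written and the correction is cheap. It is not a threat to the trial's conclusions.

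**What to change.** 1. Replace the closing re-entry sentence of SAP 9.9.1 with: *For OLE re-entry subjects, AEs that start or worsen more than 30 days after the last dose of DB study drug and before the first dose of OLE study drug are post AEs and not TEAEs.*
2. Add the same exception to the overall TEAE bullet, the general post-AE bullet and the Appendix 2 algorithm, so that late gap events do not enter the overall table.
3. Leave the Main Study bullet unchanged for re-entry subjects.

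The cost is one replaced sentence and one exception repeated in three places, with no new data or tables. It should be settled before the soft database lock and unblinding described in SAP 4.3, so that the class is not chosen with treatment known.
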